## 15.1.5. SUPPORTIVE ANALYSES OF PRIMARY EFFICACY VARIABLE

### 15.1.5.1. Responder Analysis

The primary analysis is to be supported by a responder analysis identifying the number of subjects who show a reduction from Baseline CS at PAC3 at each 10th percentile of the percentage reduction from Baseline in CS for each HDM-SPIRE treatment and placebo. The percentage reduction can only range from 0% to 100% and a subject with an increase from Baseline is not considered a responder in any percentile.

Document: TH005 SAP Version 2.docx  
 Author: [name]

Version Number: 2.0  
 Version Date: 24MAR2017

Template No: CS\_TP\_BS016 – Revision 3  
 Effective Date: 01May2012

Reference: CS\_WI\_BS005

A subject is considered a responder at the 10th percentile if they show a reduction in mean CS at PAC3 of ≥10%. In general, a subject is considered a responder at the ith percentile if they show a reduction in mean CS at PAC3 ≥i%. Where i = 10, 20, 30...,100. The rate of subjects with a reduction from Baseline of < 10% is to be included in the analysis under the following categories:

- < 0% reduction
- < 0% to < 10% reduction

Only subjects with both a Baseline and PAC3 CS are to be included in the analysis.

The response rate (%) at each 10th percentile is to be calculated as follows

- Response rate at PAC3 (%) = Number of responders / Total number of subjects with data at BAE and PAC3 \* 100

The response rate is to be presented for each 10th percentile and treatment group. The response rate is to be cumulative, meaning, if a subject is regarded as a responder in the highest percentile the same subject will also be counted as a responder in all other (lower) percentiles.

The responder status (yes or no) is to be analysed using a logistic regression model with treatment, pooled region, gender, asthma status as main effects and Baseline CS as covariate to compare the response rates of HDM-SPIRE treatment groups against placebo. Odds ratio of HDM-SPIRE/placebo with 95% confidence interval and p-value is to be presented.

The following SAS code is to be used for the logistic regression:

```
PROC LOGISTIC data=;
  CLASS treatment (ref = 'Placebo') period pooled_region gender asthma_status / PARAM = ref;
  MODEL resp (ref = 'Y') = baseline treatment period pooled_region gender asthma_status;
RUN;
```

Where **resp** refers to the derived response variable of 'Yes' or 'No' per subject.

A waterfall plot of the clinical response showing percentage change in CS from Baseline to PAC3 for each individual subject is to be plotted by treatment group.

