#### 4.6 Withdrawal of Subjects from the Study

The subjects will be informed that they have the right to withdraw from the study on their own accord at any time, for any reason and without having to state their reason and that this will not affect their future management and treatment. When a subject chooses to withdraw from the study, where possible, the Investigator will record a reason according to the following:

- Recovery/no longer experiencing symptoms of HDM allergic rhinoconjunctivitis.
- Lack of therapeutic response.
- Treatment related side effects.
- Unpleasant study procedures.
- Another disease or condition intervenes and prevents continuation in the study.
- External factors unrelated to the study.

**VERSION FINAL 4.0** CONFIDENTIAL **PAGE 29 OF 92**  The subject may also be withdrawn by the Investigator for the following reasons:

DATE 01 APRIL 2015

- Adverse events (AEs), which in the opinion of the Investigator compromises the subject's participation in the study.
- Non-compliance with study procedures.
- Lost to follow-up.
- Withdrawal of consent.
- Protocol violation.
- Termination of the study.
- Pregnancy prior to completion of administration of study medication.
- Deterioration in the subject's signs/symptoms and/or the subject develops a disease or condition prior to completion of administration of study medication that, in the opinion of the Investigator, would compromise the subject's safety in continuing in the study.
- Use of any of the prohibited therapies.

In addition to this list of general criteria for withdrawing subjects from the study dosing should immediately be discontinued (and not restarted) in the event of one or more of the following events:

- A grade 3 or 4 systemic allergic reaction (see Appendix 4)
- Two consecutive doses result in a grade 3 or 4 injection site reaction despite reduction of the dose (See Section 5.5.1)
- A serious adverse event that in the opinion of the Investigator is treatment related
- Medical necessity for a subject to use any of the contraindicated medications (see Section 5.8.5) during the treatment period.

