### 5.7 Randomisation

Subjects who successfully complete Period 1 Screening and continue to meet the study entry criteria at the end of the BAE, will be randomised to receive placebo or one of the HDM-SPIRE regimens. The Randomisation Schedule will be produced by a computer-generated algorithm by HMD Clinical.

Subjects will be randomised on an equal basis (i.e. 1:1:1:1) to placebo and each of the 3 HDM-SPIRE treatment groups.

VERSION FINAL 4.0 CONFIDENTIAL PAGE 35 OF 92

Randomisation will be stratified according to the following criteria:

DATE 01 APRIL 2015

- Current history of asthma (present or absent)
- Mean TRSS during BAE ( $<16, \ge 16$ )

Study medication packs will be assembled in accordance with the Randomisation Schedule. An interactive response technology (IRT) system will be used to allocate study medication packs to subjects, according to the randomisation and stratification schema. The Investigator or designee will also record the Subject Screening Number against the allocated randomised study pack on the Drug Accountability Record.

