## 7.2 Sample Size

The study will recruit approximately 660 subjects (approximately 165 per group). Based on the data from observational study TH003, if a mean CS of 1.6 is observed for the placebo group, and a mean CS of 1.28 for the active group, the expected treatment difference of 0.32 will be a 20% improvement from placebo. The statistical model will include the baseline CS as a covariate, taking this into account a standard deviation of 0.986 is assumed, so that a sample of 150 patients will have 80% power to detect a statistically significant difference in treatment.

Other data sources result in sample size estimates that range from 103/group (based on the TRSS data from Study TH002) through to 200/group (based on symptom scores adjusted for medication use in a study of sublingual HDM immunotherapy [Bergmann et al, 2013]). These data support the assumptions from Study TH003 and indicate that a difference of 20% between placebo and active treatment will be observed with a sample size of 150 subjects per group. It is estimated that up to 10% of subjects may drop-out before PAC3 or have missing data during PAC3. Consequently, approximately 660 subjects in total will be randomised.

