## 6.5. STATISTICAL TESTS

The default significance level is to be 5%; confidence intervals are to be 95% and all tests are to be two-sided, unless otherwise specified in the description of the analyses.

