Step 2) The missing values for each pattern is to be imputed via the chained equation method, using SAS PROC MI option MONOTONE REG. The MNAR imputation is achieved by using only appropriate study data for each pattern. For example, to impute for period PAC3 assuming that the active arm missing data has the trajectory of placebo only placebo observations up to and including PAC3 is to be used.

The following SAS code is to be used:

```
PROC MI data=imp1 SEED=<> NIMPUTE=1 OUT=imp2;
  BY _Imputation_;
  CLASS trt;
  VAR BAE0 PAC1 PAC2 PAC3;
  MONOTONE REG;

  MNAR MODEL (PAC1 / MODELOBS =(trt='Placebo'));
  MNAR MODEL (PAC2 / MODELOBS =(trt='Placebo'));
  MNAR MODEL (PAC3 / MODELOBS =(trt='Placebo'));

RUN;
```

Step 3) Analyse the resulting dataset using the same method as described in Section 15.1.3 Primary Analysis of Primary Efficacy Variable for each of the 100 imputed datasets resulting in 100 estimates of the difference in adjusted mean CS between the active HDM-SPIRE treatment groups and placebo.

Step 4) An overall result is to be obtained by combining the estimates and using SAS PROC MIANALYZE to obtain the overall result.

The following SAS code is to be used:

```
PROC MIANALYZE data = imp2;
  MODELEFFECTS estimate;
  STDERR stderr;
  BY trt period;

RUN;
```

Where **estimate** refers to each estimate of the difference in adjusted mean CS between HDM-SPIRE and placebo and **stderr** refers to the standard error of each estimate.

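### The supportive responder analysis excludes subjects without a PAC3 score and has no missing-data check, so outcome-related drop-out that differs by arm could bias it in either direction

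*SAP*

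**What the plan says.** SAP 15.1.5.1 counts responders at each 10% step of reduction in CS from Baseline to PAC3. It compares each active arm with placebo by logistic regression, giving odds ratios, 95% confidence intervals and p-values. On who is counted it says: "Only subjects with both a Baseline and PAC3 CS are to be included in the analysis". The denominator of the response rate is defined the same way.

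Protocol 7.5.3.1.2 asks for this analysis in support of the primary one. It singles out the 20% threshold, which it regards as clinically meaningful, and the 10% threshold. It does not define the denominator. Protocol 7.5.3.1.3 leaves missing data from drop-outs to the SAP.

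Protocol 4.6 lists "Lack of therapeutic response" among the withdrawal reasons, together with treatment-related side effects and also recovery. Under Protocol 6.2.2.2, subjects withdrawn from the study before the last dose go straight to Visit 5, so they have no PAC3 diary.

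SAP 15.1.4 plans a control-based imputation and repeats the primary analysis "for each of the 100 imputed datasets resulting in 100 estimates". Those estimates are of the adjusted mean CS difference. Nothing similar is planned for responder status.

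**The concern.** Subjects without PAC3 leave both numerator and denominator. The logistic model then relies on missingness being unrelated to response, given only treatment and the baseline covariates. The MMRM asks for less, because it also uses PAC1 and PAC2 from subjects who have them, and it is backed by a missing-not-at-random analysis.

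Equal drop-out cannot be taken for granted. Protocol 1.3.1 says the efficacy and tolerability of unit doses above 12 nmol are unknown, and Protocol 5.5.1 contains a tolerability route to study withdrawal. If one arm loses more non-responders than another, its response rate rises with no benefit behind it. If it loses more recovered subjects, its rate falls. The responder table is the one most easily read in clinical terms, and the plan offers no way to see how far it depends on who is missing.

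**Working it through.** **Inputs from the documents.** Significance level: "The default significance level is to be 5%; confidence intervals are to be 95% and all tests are to be two-sided" (SAP 6.5). Effect: "the expected treatment difference of 0.32 will be a 20% improvement from placebo"; variability: "a standard deviation of 0.986 is assumed" (both Protocol 7.2). Allocation: "Subjects will be randomised on an equal basis (i.e. 1:1:1:1) to placebo and each of the 3 HDM-SPIRE treatment groups" (Protocol 5.7). Randomised: 165 per group, 660 in total. Drop-out or missing PAC3: up to 10% overall (Protocol 7.2). Response rates and drop-out by arm are not given, so every such figure below is an assumption.

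**1. The plan's own figure.** n per group = 2 × (1.960 + 0.842)² × SD² / difference² ≈ 2 × 7.849 × 0.9722 / 0.1024 ≈ 149.0, rounded up to 150. The statement "so that a sample of 150 patients will have 80% power to detect a statistically significant difference in treatment" therefore reproduces, read as 150 per group. Power at 150 is 80.3% by the normal approximation and 80.0% by the noncentral t. This concerns mean CS; no power is stated for the responder analysis. If the 10% allowance is used in full, 0.10 × 660 = 66 subjects, or 16.5 per group, would lack PAC3 and leave the responder table.

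**2. Equal drop-out, all non-responders.** Let p be the response rate among all randomised subjects and d the share without PAC3. The observed rate is p / (1 − d). With d = 10% in both arms and p = 40% in both, each arm shows 0.40 / 0.90 = 44.4%. There is no false difference. With true rates of 40% and 50%, the observed rates are 44.4% and 55.6%, and the odds ratio moves only from 1.50 to 1.56.

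**3. Unequal drop-out, all non-responders, no true effect.** Placebo d = 5%, active d = 15%:

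| p | Placebo, p/0.95 | Active, p/0.85 | Difference (points) | Odds ratio | False-positive rate |
|---|---|---|---|---|---|
| 30% | 31.6% | 35.3% | 3.7 | 1.18 | about 10% |
| 40% | 42.1% | 47.1% | 5.0 | 1.22 | about 14% |
| 50% | 52.6% | 58.8% | 6.2 | 1.29 | about 19% |

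The last column is for an unadjusted two-sided 5% normal test starting from 165 per arm. The planned model is adjusted, so these rates are indicative.

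**4. Opposite case: every drop-out would have been a responder.** The observed rate is (p − d) / (1 − d). With p = 40%, placebo shows 0.35 / 0.95 = 36.8% and active 0.25 / 0.85 = 29.4%. The false difference is −7.4 points.

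**5. Drop-outs respond like completers, 40% in each arm.** The complete-case difference is 0. Counting missing as non-response gives 0.40 × 0.85 − 0.40 × 0.95 = 0.34 − 0.38 = −4 points. That rule is therefore an extreme and not a neutral default.

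**6. Spread across methods.** Suppose completers respond at 50% on active and 40% on placebo, with 15% and 5% missing.
- Complete case: 10 points.
- Missing active subjects respond at the placebo rate: 0.85 × 0.50 + 0.15 × 0.40 − 0.40 = 8.5 points.
- Missing as non-response: 0.50 × 0.85 − 0.40 × 0.95 = 0.425 − 0.380 = 4.5 points.

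**The case against.** The strongest reply is that little depends on this table. It is one of several supportive analyses, beside the per-protocol repeat, the control-based analysis, the region interaction and four alternative score weightings. Its p-values lie outside the step-down procedure of SAP 7.4. The protocol leaves the denominator open, so the SAP contradicts nothing. All of this stands, and it limits the weight of the point.

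The contrast with the MMRM is also narrower than it looks. PAC1 starts at week 18, so a subject who leaves the study earlier contributes no post-baseline score to either analysis. The two differ only for subjects with PAC1 or PAC2 but no PAC3. Protocol 4.6 says that stopping treatment need not mean leaving the study. Under SAP 7.3 a single complete PAC3 diary day is enough for a PAC3 mean. Both reduce the number excluded.

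A reader might infer that the rule favours the active arms. The documents do not support that: recovery is a listed withdrawal reason, no drop-out by arm is given, and step 4 reverses the sign. Drop-out that depends on arm alone, or on outcome alone, leaves the odds ratio unbiased apart from covariate adjustment. Bias needs outcome-related drop-out that differs by arm.

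Finally, the 15.1.4 imputations cannot be reused as written, because the code has errors and the listed variables omit region, gender and asthma status. That also stands and raises the cost somewhat. None of these replies supplies a missing-data check for responder status.

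**Conclusion.** The concern holds as a gap in a supportive analysis. The responder comparison is complete-case, its exclusions may be linked to outcome, and no sensitivity analysis is planned for it. Under the assumed 5% versus 15% drop-out, with all drop-outs non-responders and no true effect, the false difference is 3.7 to 6.2 points for true response of 30% to 50%. With equal 10% drop-out of non-responders it is zero. The direction in the actual trial cannot be known from the documents.

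A reader might also infer that the primary result is weakened. It is not: the MMRM uses all available PAC means, has its own missing-not-at-random analysis, and alone carries the type I error control. The change is a cheap improvement and does not correct the primary analysis.

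**What to change.** In SAP 15.1.5.1, keep the complete-case table and add the following before unblinding:

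- An all-ITT version for subjects with a Baseline CS, at least at the 10% and 20% thresholds. Derive responder status in each of the 100 control-based imputed datasets, fit the logistic model in each, and combine the log odds ratios and their standard errors with `PROC MIANALYZE`.
- A version with missing PAC3 counted as non-response, labelled as an extreme case.
- The number without PAC3 and the reasons, by arm.

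Correct the code before reusing it:

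- The baseline variable is `BAE` in Step 1 of SAP 15.1.4 and `BAE0` in Step 2.
- `PROC MIANALYZE` reads `imp2`, the imputed data, where it needs the dataset of estimates and standard errors.
- In the logistic code, `ref='Y'` makes response the reference level, so non-response is modelled.
- `period` appears in the logistic code although the model uses PAC3 only and the text does not list it.

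Decide at the same time whether region, gender and asthma status belong in the imputation model. The cost is a little programming and two more sets of results. Response rates may look slightly less favourable than in the complete-case table.

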**PROC MIXED data= IC INFO;**

```
CLASS subject treatment period pooled_region gender asthma_status;
MODEL CS=baseline treatment period pooled_region gender asthma_status treatment*period
baseline*period / DDFM=KR;
ESTIMATE '4 x 12 nmol HDM-SPIRE vs Placebo at PAC3' treatment 1 0 0 -1
treatment*period 0 0 1 0 0 0 0 0 0 0 -1 / CL;
REPEATED period / SUBJECT=subject TYPE=UN;
```

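### The responder logistic code in SAP 15.1.5.1 does not match its text: it takes response as the reference level, names a level the SAP does not give, and adds a period term

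*SAP*

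**What the plan says.** SAP 15.1.5.1 calls a subject a responder at a threshold of i% if mean CS at PAC3 is at least i% below Baseline ("Where i = 10, 20, 30...,100"). The set is restricted: "Only subjects with both a Baseline and PAC3 CS are to be included in the analysis". Responder status is then analysed with a "logistic regression model with treatment, pooled region, gender, asthma status as main effects and Baseline CS as covariate", and the stated aim is to compare response rates between each regimen and placebo. On reporting: "Odds ratio of HDM-SPIRE/placebo with 95% confidence interval and p-value is to be presented".

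The SAP introduces the program as an instruction: "The following SAS code is to be used for the logistic regression". Its model statement is "MODEL resp (ref = 'Y') = baseline treatment period pooled_region gender asthma_status". The CLASS statement sets placebo as the treatment reference and also lists period. The line beneath the code says that resp "refers to the derived response variable of 'Yes' or 'No' per subject".

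Protocol 7.5.3.1.2 treats a reduction of 20% or more as clinically meaningful. It asks for a test of proportions against placebo at that level and at 10%.

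**The concern.** Text and code in one subsection describe different analyses, and the code is the part that is mandated. There are three differences.

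1. **Direction.** The text is about response rates, but the code takes response as the reference level and so models non-response.
2. **Label.** The code asks for a level 'Y'. The SAP says the levels are 'Yes' and 'No'.
3. **Terms.** The code has period in CLASS and MODEL. The text model does not.

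This logistic model is the only test the SAP states for the response rates that the protocol singles out. An odds ratio of 0.58 labelled HDM-SPIRE/placebo would be read as active treatment lowering the chance of response when it raised it. The same could happen at every threshold from 10% to 100%.

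**Working it through.** The documents give no response rates and no expected odds ratio for this analysis, so there is no figure of the plan's to reproduce. The check is a comparison of text with code, then an illustration on assumed rates.

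**Text against code**

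| Item | Text of 15.1.5.1 | Code of 15.1.5.1 |
|---|---|---|
| Quantity compared | Response rates | Non-response, because `ref=` on a binary response names the reference level and the other level is modelled |
| Levels of resp | Yes / No | 'Y' |
| Treatment contrast | HDM-SPIRE/placebo | Placebo as reference (agrees) |
| Terms | Treatment, pooled region, gender, asthma status, Baseline CS | The same, plus period |

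The direction and label problems are alternatives. With Y/N coding the code runs and is reversed. With Yes/No coding the label matches nothing. Changing the label to `ref = 'Yes'` and nothing else brings the reversal back.

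The extra term also appears in the primary-analysis code of SAP 15.1.3, "MODEL CS=baseline treatment period pooled_region gender asthma_status treatment*period", where three periods are analysed and period belongs.

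**Size of the reversal (Y/N coding, one row per subject)**

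Inputs: 150 subjects per arm, the completer number in Protocol 7.2, and response rates that I assume. No covariates.

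Formulas: OR = [a/(n−a)] / [c/(n−c)], with a and c the responders on active and placebo; SE(log OR) = √[1/a + 1/(n−a) + 1/c + 1/(n−c)]. Modelling non-response inverts the OR and its limits and leaves SE and p unchanged.

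- 30% against 20% (45 and 30 responders): OR = (45/105)/(30/120) = 1.714. SE = √(1/45 + 1/105 + 1/30 + 1/120) = 0.2709. 95% CI 1.008 to 2.916, p=0.0467. As coded: 1/1.714 = 0.583 (0.343 to 0.992), p=0.0467.
- 50% against 40% (75 and 60 responders): OR = (75/75)/(60/90) = 1.500. SE = √(1/75 + 1/75 + 1/60 + 1/90) = 0.2333. 95% CI 0.949 to 2.370, p=0.0823. As coded: 0.667 (0.422 to 1.053), p=0.0823.

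The same holds with covariates. On simulated data (four arms of 150, with the covariates of the SAP text), modelling response gave odds ratios of 2.117, 1.573 and 1.836. Modelling non-response gave 0.472, 0.636 and 0.545. The p-values were identical: 0.0018, 0.0569 and 0.0110.

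**Effect of the period term**

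- *PAC3 rows only.* Period is constant, so it adds no information. In the simulated design a constant column leaves the rank at 15 with 16 columns.
- *PAC3 status repeated on three period rows.* The model would treat the rows as independent, so the SE is multiplied by 1/√3 = 0.577. For 30% against 20%, SE is 0.1564 and p goes from 0.047 to 0.0006. For 50% against 40%, SE is 0.1347 and p goes from 0.082 to 0.0026. With no treatment effect, a nominal 5% test rejects with probability 2[1 − Φ(1.96/√3)] = 0.258. Simulation of 200,000 trials gave 0.257 at a 20% response rate and 0.263 at 40%, against 0.048 and 0.052 with one row per subject.

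The behaviour of `ref=` is reasoned from the meaning of the option and checked with an equivalent logistic fit. The code was not run in SAS, so I say only that an unmatched level may stop it.

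**The case against.** The strongest reply is that little follows in practice.

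- **The reversal needs a coding the SAP does not state.** With Yes/No levels, the code as written gives no reciprocal odds ratio. This is correct, and the reversal figures are conditional on Y/N coding or on a label-only repair. Neither branch gives the analysis the text describes.
- **No sentence says that the odds are odds of response.** The text fixes the treatment contrast, and the code respects it. This also stands, but the stated purpose of comparing response rates leaves no other natural reading.
- **The three-row layout is not in the plan.** The subsection defines response at PAC3, per subject, with one denominator. I agree that this points against repeated rows, though the row structure is not stated. The inflated error rate is therefore a conditional risk, and on the likely layout the period term is harmless.
- **The error would be seen.** Rates are tabulated by arm and threshold, so an odds ratio below 1 beside a higher active rate would stand out, and a failed run would be noticed. That is probable. The repair would then depart from code the SAP says is to be used, possibly after unblinding.
- **A separate fit per threshold is already implied.** Largely so. The table templates mentioned in SAP section 8 are not among the documents and may show it. One sentence would settle it.
- **The analysis is supportive and p-values do not change under reversal.** Both are true, and they limit how serious this is.

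**Conclusion.** The concern holds. The prescribed code is wrong as written for the analysis the text describes. It either gives treatment odds ratios in the opposite direction (Y/N coding) or may not run (the stated Yes/No coding), and it carries a term the text model does not have.

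Under Y/N coding an intended odds ratio of 1.71 prints as 0.58, and 1.50 as 0.67. Those values rest on assumed response rates and 150 per arm; the reciprocal relation does not. The rejection rate of about 26% applies only if PAC3 status is repeated on three rows, which the text points against.

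The analysis lies outside the step-down procedure. The primary MMRM, the response-rate table and the waterfall plot are not affected. The correction should be made before the responder analysis is run, but it does not bear on the trial's main conclusion.

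**What to change.** In the responder code of SAP 15.1.5.1:

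- Replace `(ref = 'Y')` on the response with `(event = 'Yes')`, and make the label match the derived variable exactly.
- Delete `period` from both the CLASS and MODEL statements, so that the terms match the text.
- Add a sentence stating that the input has one PAC3 row per subject and that the model is fitted separately at each threshold. It would help to say there that the odds are odds of response.

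The cost is two lines of code and one sentence. Data collection, the analysis set and the primary analysis do not change.
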